2. STUDY PROTOCOL

This was a prospective comparative clinical study to be conducted at one clinical site located in the United States. Three Nidek Mirante devices, three Optovue RTVue XR Avanti devices and one OPTOS P200DTx will be used. For agreement and precision analysis of OCT scans and agreement analysis of image quality of OCT ACA scans, each Nidek Mirante device will be paired with one of the Optovue RTVue XR Avanti devices. One device operator will be assigned to each device pair to create three distinct operator/device configurations.

For agreement analysis of SLO image quality, one OPTOS P200DTx will be included in one of three operator/device configurations.

Both eyes of normal subjects must meet all inclusion and none of the exclusion criteria in order for the subject to be enrolled in the study. Eligible subjects will be randomized to testing sequence of devices, the starting device (Nidek Mirante, Optovue RTVue XR Avanti or OPTOS P200DTx) and for the normal subject population, the study eye. For subjects in the glaucoma, retinal disease or corneal groups, the investigator will select the study eye based on presence of qualifying pathology. [REDACTED]

The Nidek Mirante, Optovue RTVue XR Avanti, and OPTOS P200DTx will be used in accordance with this clinical protocol and each device's User Manual.

Normal, glaucoma, and retinal disease subjects as well as corneal disease subjects enrolled to obtain measurements to demonstrate both agreement and precision will be randomized to the device configuration order and to the starting device within each configuration. Separate randomization schedules will be created for each subject population group (normal, glaucoma, retinal disease and corneal disease).

Corneal disease subjects enrolled to obtain only measurements to demonstrate qualitative agreement will be assessed at configuration 3 (C3) only and randomized using the next available corneal disease group randomization with C3 starting configuration to assign subject ID and starting device.

[figure not shown]
[figure not shown]
The device order will be randomly assigned as one of 2 sequences of Device (D), with D1: Test: Nidek Mirante and D2: Control: Optovue RTVue XR Avanti (OCT) and OPTOS P200DTx (SLO).

For the configurations with OPTOS P200DTx, the SLO scans for both devices will be taken after the OCT scans are completed for both devices. The SLO scans will be obtained in the same device order as for OCT.

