3. STATISTICAL ANALYSIS PLAN

Analysis of Agreement Endpoints

Analysis of the agreement study endpoints will include measurements from Nidek Mirante and the predicate device. Descriptive statistics of each agreement study endpoint will be provided by subject population for each device.

Analysis of the agreement study endpoints of the scan size and tracing HD functions will include measurements from one Nidek Mirante and be analyzed in the same fashion as detailed above.

Analysis of Precision Endpoints

Analysis of the precision study endpoints will include measurements from the Nidek Mirante and predicate device, summarizing the precision results in units measured and as a percentage of the mean across all eyes (% CV). Plots of the within-eye SD for each machine versus the within-eye mean will be provided with different symbols for the two different device types.

[REDACTED]

[REDACTED]

[REDACTED]

Analysis of the Image Quality Assessments

The number of eyes with unacceptable and acceptable image quality will be summarized and compared by device, subject population and for all subjects.

The first acceptable ACA images captured by the Mirante and Optovue RTVue XR Avanti will be compared to assess image quality.

The first acceptable SLO image captured by the Mirante and P200DTx will be compared to assess image quality.

[REDACTED]

[REDACTED]

[REDACTED]

[REDACTED]

Analysis of Safety Endpoints

Adverse events reported will be listed by subject.

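### Does letting the investigator choose the study eye in the diseased groups make precision and image quality look better than they are?

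*Combined protocol and SAP*

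**What the plan says.** Section 2 (Study Protocol) treats the study eye in two ways. Normal subjects enter only if both eyes are eligible ("Both eyes of normal subjects must meet all inclusion and none of the exclusion criteria"), and the items randomized include, "for the normal subject population, the study eye". The other rule opens "For subjects in the glaucoma, retinal disease or corneal groups" and continues that "the investigator will select the study eye based on presence of qualifying pathology". A redacted block comes next, in the same paragraph. The inclusion and exclusion criteria to which Section 2 refers are not in the readable text.

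The same section pairs each Mirante with one Avanti under one operator. Subjects who contribute to both agreement and precision "will be randomized to the device configuration order and to the starting device within each configuration". Corneal subjects enrolled only for qualitative agreement are seen in the third configuration, with the starting device taken from the corneal randomization schedule.

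Section 3 (Statistical Analysis Plan) reports precision for both device types in measured units and as % CV, with plots of within-eye SD against within-eye mean. On image quality it states: "The number of eyes with unacceptable and acceptable image quality will be summarized and compared by device, subject population and for all subjects".

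**The concern.** Presence of pathology is a yes/no criterion. It settles the study eye when one eye qualifies and says nothing when both do. Read alone, the sentence then leaves the choice to the investigator, who may know which eye has clearer media, steadier fixation or milder disease. The protocol randomizes the eye in normals, where two eyes are always available, so the mechanism exists and appears not to be used in the groups where selection could matter more.

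At stake would be the absolute results in diseased eyes, namely within-eye SD, % CV and counts of acceptable images. These would describe a chosen eye, not a typical one, and the all-subjects image-quality summary would mix randomly chosen normal eyes with investigator-chosen diseased eyes.

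**Working it through.** The readable text gives no sample size, SD, image-quality rate or share of subjects with two qualifying eyes, so there is no stated figure to reproduce. The check is first a reading of the text, then a bound on assumed inputs.

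**1. Is a rule for two qualifying eyes missing?** The sentence on investigator selection is followed at once by redacted text, a natural place for further study-eye rules. The criteria defining qualifying pathology, which could also restrict bilateral cases, are not visible. Redacted content does not count as absent from the plan, so the premise cannot be established.

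**2. Is the direction supported?** The only stated ground for selection is pathology. Nothing readable mentions media clarity, fixation or ease of scanning. An investigator with discretion could equally take the eye with the more definite or more advanced disease, and results would then look worse.

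**3. Is the difference from normals a defect?** Both eyes of a normal subject must qualify, so either can be drawn at random. No such requirement is readable for diseased subjects, and randomizing the eye in all of them could assign an eye without the pathology under study. Different rules are to be expected.

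**4. Does selection reach the device comparison?** Section 2 names one study eye per subject, and the devices are paired within each configuration. If an eye's difficulty multiplies both devices' within-eye SDs by the same factor k, then (k × SD_Mirante) / (k × SD_Avanti) = SD_Mirante / SD_Avanti. The ratio changes only if difficulty affects the two devices differently, and nothing in the documents indicates that.

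**5. How large could the effect on absolute figures be?** All inputs here are assumed, and the better eye is always picked, so these are upper bounds for given inputs.

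*Latent difficulty.* For two standard normal eye scores with correlation r, the better eye differs from a random eye by √((1 − r)/π). With r = 0.5 this is √(0.5/π) = 0.399 SD. With 50% to 80% of subjects bilateral, the group shift is 0.5 × 0.399 = 0.20 to 0.8 × 0.399 = 0.32 SD. The arithmetic is right, but the scale is neither within-eye SD nor an acceptance rate, so it sizes no planned endpoint.

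*Image quality.* Let q be the per-eye unacceptable rate, b the share of subjects with two qualifying eyes, and ρ the between-eye correlation. The rate with the better eye chosen is (1 − b)q + b[q² + ρq(1 − q)]. For q = 0.10 the bracket is 0.01 + 0.3 × 0.09 = 0.037 at ρ = 0.3, and 0.01 + 0.7 × 0.09 = 0.073 at ρ = 0.7. At b = 0.5 the rates are 0.05 + 0.5 × 0.037 = 6.85% and 0.05 + 0.5 × 0.073 = 8.65%.

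*Precision.* Eye-specific within-eye SDs were simulated as log-normal (SD on the log scale 0.2 to 0.4, between-eye correlation 0.3 to 0.7), taking the smaller SD in bilateral subjects. The ratio is pooled SD with selection over pooled SD for a random eye.

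| Share bilateral (b) | Unacceptable rate when q = 10% | Pooled SD ratio |
|---|---|---|
| 0% | 10% | 1 |
| 25% | 8.4% to 9.3% | 0.953 to 0.985 |
| 50% | 6.9% to 8.7% | 0.904 to 0.969 |
| 75% | 5.3% to 8.0% | 0.852 to 0.953 |

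*Opposite choice.* The better-eye and worse-eye rates average to q. If the worse eye were always taken at b = 0.5, the rate would be 2 × 10% − 6.85% = 13.15% at ρ = 0.3 and 2 × 10% − 8.65% = 11.35% at ρ = 0.7. The same assumptions thus give a shift of equal size either way, and the documents do not determine its sign.

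**The case for a change.** The strongest reply is that the readable sentence names the investigator as selector on a criterion that cannot separate two qualifying eyes, while the readable list of randomized items confines eye randomization to normals. That makes a random tie-break in the redacted text less likely. Pairing protects the device contrast but not the absolute precision and acceptability figures that Section 3 will report. Separate randomization schedules already exist for each population, so a random choice would cost little.

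Part of this stands. The readable text contains no tie-break, and pairing does not protect absolute figures. But a tie-break need not be random. A fixed clinical or anatomical rule would also remove discretion, and it could sit in the redacted block or in the eligibility criteria. The absolute effect also requires systematic choice of the easier eye, for which there is no textual support. As for mixing random and chosen eyes, the image-quality sentence in Section 3 can be read as device comparisons within each population and overall, which does not set normals against diseased eyes.

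A sensitivity analysis limited to subjects with one qualifying eye would not settle the matter. Unilateral and bilateral disease may differ in type and severity, so a difference in that subset would not isolate the investigator's choice.

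**Conclusion.** The concern does not hold. It depends on the absence of a rule for two qualifying eyes, which cannot be asserted when redacted text follows the sentence and the eligibility criteria are not visible. It also depends on a preference for the easier eye, which nothing readable supports. The different treatment of normals follows from the requirement that both their eyes qualify. The Mirante-versus-Avanti precision ratio is unaffected so long as eye difficulty acts alike on both devices.

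The possible effect on absolute figures runs from zero (no bilateral subjects, or a rule that fixes the eye) to the bounds tabulated above. Those bounds rest wholly on assumed rates, correlations and perfect picking, so they do not measure a bias in this trial. What is left is a request that the sponsor confirm how the eye is chosen when both qualify. That is a point of detail and does not show a flaw in the design.

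### Corneal subjects seen only at C3 use up C3-first rows of the one corneal randomization list, so C3 tends to be tested later in corneal precision subjects unless rows are reserved or they enrol last

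*Combined protocol and SAP*

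**What the plan says.** All of the allocation rules are in section 2, Study Protocol.

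- **Configurations.** "One device operator will be assigned to each device pair to create three distinct operator/device configurations".
- **Lists.** "Separate randomization schedules will be created for each subject population group (normal, glaucoma, retinal disease and corneal disease"). The visible text therefore has one corneal list.
- **Corneal subjects contributing to agreement and precision.** They are "randomized to the device configuration order and to the starting device within each configuration".
- **Corneal subjects contributing only to qualitative agreement.** They "will be assessed at configuration 3 (C3) only" and are "randomized using the next available corneal disease group randomization with C3 starting configuration to assign subject ID and starting device".
- **Device order.** "The device order will be randomly assigned as one of 2 sequences of Device (D").

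Section 3, Statistical Analysis Plan, reports precision for both device types, "summarizing the precision results in units measured and as a percentage of the mean across all eyes (% CV"). The three blocks that follow that paragraph are redacted.

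The visible text gives no subgroup sizes, block size, list length or enrolment order. It does not mention reserved or replacement rows, or a second corneal list.

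**The concern.** Two kinds of corneal subject draw on one list. Precision subjects take whichever row comes next. Qualitative-only subjects skip ahead to the next row that starts with C3. Because that row also supplies the subject ID, it is spent, and the remainder of its configuration order is never used.

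The rule therefore takes rows selectively. It removes C3-first rows, some or all of them, from the part of the list that precision subjects would have reached. C3 then falls in second or third position more often than C1 and C2 do.

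Each configuration is one operator with one pair of devices, and randomizing the order keeps differences between configurations separate from effects of testing position such as fatigue. If C3 is systematically late, the two are partly confounded in corneal precision subjects, which is one of the four populations. What is at stake is the configuration component of corneal precision. Mirante-versus-control agreement is not at stake, because both devices are used within every configuration and the starting device is randomized there.

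**Working it through.** **Inputs.** From section 2: three configurations, one corneal list, and the two ways of drawing from it. Assumed: a balanced list in which one third of rows start with C3, and the subgroup sizes P (precision) and Q (qualitative-only). The plan states no figure to reproduce.

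**Step 1, limits on the C3-first share.**

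- Qualitative-only subjects enrol last: precision subjects use an untouched list, so the share is 1/3.
- Qualitative-only subjects enrol first: they take Q C3-first rows, which lie within about the first 3Q rows and leave 2Q rows that do not start with C3. Precision subjects use those 2Q rows and then P − 2Q rows of normal mix. C3-first orders left = (P − 2Q)/3, so share = max(0, (1 − 2Q/P)/3).
- Q/P = 0.10: (1 − 0.20)/3 = 27%. Q/P = 0.25: (1 − 0.50)/3 = 17%. Q/P = 0.50 or more: 0%.

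**Step 2, simulation of the rule.** Six orders in permuted blocks of 6. Expected C3-first share among precision subjects:

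| Assumed P + Q | Q last | Randomly mixed | Q first |
|---|---|---|---|
| 20 + 2 | 0.332 | 0.274 | 0.267 |
| 24 + 6 | 0.333 | 0.185 | 0.167 |
| 40 + 10 | 0.334 | 0.180 | 0.166 |
| 30 + 10 | 0.333 | 0.136 | 0.111 |
| 20 + 10 | 0.332 | 0.080 | 0.000 |
| 40 + 20 | 0.333 | 0.057 | 0.000 |

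Mixed enrolment lies close to the lower limit. A three-order Latin square behaves in the same way (24 + 6: mixed 0.183, first 0.167). Reserving rows for the qualitative-only subjects keeps the share at 0.333.

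**Step 3, mean testing position of C3.** With share s and the remainder split evenly between second and third, m = s + 2.5(1 − s) = 2.5 − 1.5s. The three mean positions sum to 6, so C1 and C2 each average (6 − m)/2.

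- 24 + 6 mixed: m = 2.5 − 1.5 × 0.185 = 2.22, against 1.89 for C1 and C2.
- 20 + 10 mixed: m = 2.38, against 1.81.
- 20 + 10 first: m = 2.50, against 1.75.

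**Step 4, list length.** For 24 + 6 mixed, about 4.4 of the 24 precision subjects start at C3 whether the list has 30, 42, 60 or 240 rows, against 24/3 = 8 when balanced. Extra rows do not help because the rule takes rows from the front. Enrolling last also needs enough rows. A 30-row list has 10 C3-first rows, precision subjects use 8, and 2 remain for 6 people, so 4 have none. With 42 rows there are 14, and 14 − 8 = 6 suffices.

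**Step 5, what could happen to the precision SD (illustration only).** Assume repeatability SD 1, C3 truly different from C1 and C2 by d = ±1, an order effect of 0.5 per position, and no order term in the model.

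- Without any order effect: variance 1 + 1/3, SD √(4/3) = 1.155. Imbalance then changes nothing.
- Order effect with balanced order: 1 + 1/3 + 0.25 = 1.583, SD 1.26 (+9%).
- Order effect with imbalance: variance 1.583 + 0.5·d·(m − 2). At m = 2.38 this is 1.583 ± 0.19, SD 1.33 or 1.18. At m = 2.50 it is 1.583 ± 0.25, SD 1.35 or 1.15. At m = 2.22 it is 1.583 ± 0.11, SD 1.30 or 1.21.
- With d = 0: 1 + 0.25, SD 1.12 whatever the imbalance.

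Simulation for 20 + 10 gives the same values. When testing position is added as a fixed effect, total SD returns to 1.16–1.17 and the configuration variance to 0.33–0.35 (order-free value 1/3) under every enrolment pattern.

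**The case against.** The strongest reply is that the public text cannot show harm. Two figures that follow the rule are missing, and text is redacted both in the randomization section and directly under the precision analysis. Any of these could contain a reservation rule, an enrolment order or a position term. This stands: the point closes if they do.

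The sizes are also assumed, and the possible C3-first share runs from no loss to complete loss, so this trial cannot be placed within that range. This also stands.

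Harm needs several conditions together: qualitative-only subjects not last and without reserved rows, Q not small relative to P, a real position effect, a model that omits it and, for total SD to move, a true difference at C3. None is demonstrated. Even under the assumed order effect, most of the excess SD is present with balanced order (1.26 against 1.155). Imbalance then moves it by about 6% either way for 20 + 10 mixed and about 3.5% for 24 + 6 mixed, and in one direction it brings the estimate closer to the order-free value. All of this is accepted, and it limits the severity.

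Finally, Mirante and the control share the same configuration orders, so the imbalance is common to both. That gives partial shelter to a comparison of the two precision estimates. It does not protect the precision figures reported for each device, and the shift can differ between devices if C3 deviates differently on each.

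None of this removes the mechanism. The selective draw is a stated rule that works against the plan's own randomization of configuration order.

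**Conclusion.** The concern holds, as a minor point. On the visible text, qualitative-only corneal subjects deplete C3-first orders for corneal precision subjects unless they enrol last with enough C3-first rows remaining, or rows are set aside for them. The expected C3-first share then lies between max(0, (1 − 2Q/P)/3) and 1/3, and random mixing of the two subgroups puts it near the lower end. This rests on a balanced list with one third of rows starting at C3. The subgroup sizes used above are assumptions.

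The consequence is confined to the configuration component of corneal precision, and it arises only with an order effect that the model does not include. Total reproducibility SD moves appreciably only if C3 also truly differs from C1 and C2. The documents do not allow the size or direction of that shift to be determined, and none is claimed.

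**What to change.** **Before enrolment:** give qualitative-only corneal subjects their ID and C3 starting device from a separate list balanced on the two device sequences, and keep the corneal schedule for subjects who visit all three configurations. Cost: one list and one protocol sentence.

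**If enrolment has begun or ended** (section 2 opens with "This was a prospective comparative clinical study to be conducted at one clinical site", which mixes past and future): tabulate the achieved configuration order for corneal precision subjects. If the precision model does not already include it, add testing position (1st, 2nd, 3rd) as a fixed effect in a sensitivity analysis. Cost: one table and one analysis.

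Neither route adds subjects or visits. If rows were already reserved, or the qualitative-only subjects enrolled last with enough C3-first rows left, one sentence saying so closes the point.

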3. STATISTICAL ANALYSIS PLAN

Analysis of Agreement Endpoints

Analysis of the agreement study endpoints will include measurements from Nidek Mirante and the predicate device. Descriptive statistics of each agreement study endpoint will be provided by subject population for each device.

Analysis of the agreement study endpoints of the scan size and tracing HD functions will include measurements from one Nidek Mirante and be analyzed in the same fashion as detailed above.

Analysis of Precision Endpoints

Analysis of the precision study endpoints will include measurements from the Nidek Mirante and predicate device, summarizing the precision results in units measured and as a percentage of the mean across all eyes (% CV). Plots of the within-eye SD for each machine versus the within-eye mean will be provided with different symbols for the two different device types.

[REDACTED]

[REDACTED]

[REDACTED]

Analysis of the Image Quality Assessments

The number of eyes with unacceptable and acceptable image quality will be summarized and compared by device, subject population and for all subjects.

The first acceptable ACA images captured by the Mirante and Optovue RTVue XR Avanti will be compared to assess image quality.

The first acceptable SLO image captured by the Mirante and P200DTx will be compared to assess image quality.

[REDACTED]

[REDACTED]

[REDACTED]

[REDACTED]

Analysis of Safety Endpoints

Adverse events reported will be listed by subject.

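### The agreement subsection names only per-device descriptive statistics, which give the mean bias but not the spread of within-eye differences that the paired design can supply

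*Combined protocol and SAP*

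**What the plan says.** The SAP's subsection on agreement endpoints (section 3) first says which data enter: "Analysis of the agreement study endpoints will include measurements from Nidek Mirante and the predicate device". It then names one output: "Descriptive statistics of each agreement study endpoint will be provided by subject population for each device". A second paragraph covers the scan-size and tracing-HD functions. It says that these endpoints "will include measurements from one Nidek Mirante and be analyzed in the same fashion as detailed above", and so adds no further method. The visible subsection mentions no within-eye difference, limits of agreement, confidence interval, regression or acceptance criterion, and it carries no redaction mark.

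Section 2 describes the design. For the OCT agreement and precision work, "each Nidek Mirante device will be paired with one of the Optovue RTVue XR Avanti devices", and one operator runs each pair, which gives three configurations. On order within a configuration it says "The device order will be randomly assigned as one of 2 sequences of Device (D"), with the Mirante as test device and the Avanti as OCT control. There is a designated study eye. It is chosen by randomization in normal subjects and by the investigator, on qualifying pathology, in the disease groups. Subjects who contribute to both agreement and precision are randomized to the order of the configurations and to the starting device within each.

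**The concern.** Agreement with the control device is a stated purpose of pairing the machines. The pairing yields a test-minus-control difference for each eye, and agreement is a question about those differences: their average, and how widely they scatter. A table of means and SDs for each device separately addresses the first part and leaves out the second. Two devices could match on average and still disagree substantially in individual eyes, and the table would not show it.

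If the subsection is followed as it reads, the analysis does not use the pairing that the design provides. Any agreement statistic added later would also be chosen after the data are available.

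**Working it through.** The documents state no sample size, SD, correlation or agreement margin, so there is no figure of the plan's own to reproduce. What can be checked is whether per-device summaries determine the spread of within-eye differences.

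**1. General relation.** Let the device SDs be s1 and s2 and the between-device correlation r. For complete pairs:

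- mean difference = difference of the two device means, which can be read from the per-device table;
- SD of differences = sqrt(s1² + s2² − 2·r·s1·s2), which needs r, and r is not in the table.

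With equal SDs this becomes SD of differences = SD·sqrt(2(1 − r)).

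**2. Illustration.** All inputs are assumed: device means 100 and 103 (bias 3), SD 10 on each device, normal differences. The 10-unit threshold is also arbitrary.

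- 95% limits = 3 ± 1.96 × SD of differences.
- Share of eyes differing by more than 10 units = Φ((−10 − 3)/SD of differences) + 1 − Φ((10 − 3)/SD of differences).

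| Correlation | SD of differences | 95% limits | Share beyond 10 units |
|---|---|---|---|
| 0.99 | 1.41 | 0.2 to 5.8 | under 0.1% |
| 0.95 | 3.16 | −3.2 to 9.2 | 1.3% |
| 0.90 | 4.47 | −5.8 to 11.8 | 6.1% |
| 0.80 | 6.32 | −9.4 to 15.4 | 15.4% |
| 0.50 | 10.00 | −16.6 to 22.6 | 33.9% |

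The per-device table is the same in every row. For example, at r = 0.90: 10 × sqrt(0.20) = 4.47, and 3 ± 1.96 × 4.47 gives −5.8 to 11.8.

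**3. Sensitivity to the assumed SD.** With SD 5 the limits go from 1.6 to 4.4 (r = 0.99) to −6.8 to 12.8 (r = 0.50). With SD 15 they go from −1.2 to 7.2 to −26.4 to 32.4. The ratio of widths at r = 0.50 and r = 0.99 is sqrt(0.50/0.01) = 7.1 whatever the SD. It does depend on which two correlations are compared. Unequal SDs do not remove the problem: with SDs 1 and 1.2, the SD of differences runs from 1.562 at r = 0 to 0.253 at r = 0.99.

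**4. Check by re-pairing.** Sixty eyes were simulated on two devices, and the second device's values were then reassigned among the eyes. The per-device statistics are unchanged by construction (means −0.049 and −0.054, SDs 0.871 and 0.868), and so is the mean difference of 0.005. The SD of differences was 0.083 under the first pairing and 1.184 under the second, a ratio of about 14 (1.184/0.083).

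The per-device summaries therefore fix the bias and leave the spread of within-eye differences undetermined.

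**The case against.** The strongest reply is that the public text is a redacted extract. Section 3 has seven redacted blocks: three after the precision text and four after the image-quality text. Section 2 has another, and material ahead of section 2 was removed. Section 2 treats OCT agreement and precision as work on the same device pairs, so a shared method placed after both headings is plausible. Nor does the quoted sentence say that descriptive statistics are the only agreement analysis. This much stands: a reader might infer that the full plan has no paired analysis, and the documents do not support that.

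It does not remove the point. No redaction mark sits in the agreement subsection, and its second paragraph refers back to what stands above it as the method. Within section 3, that is only the two visible sentences. If a paired method sits under a later heading, the visible agreement text does not point to it.

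A reader might also infer a deliberate omission, because the precision text uses within-eye SDs and image quality is compared by device. That is not supported either. The precision plots show the within-eye SD for each machine, which describes repeatability within a machine. The image-quality comparison concerns image acceptability and quality. Neither is an analysis of between-device measurement differences, so neither shows that the authors specified such an analysis elsewhere and left it out here. For the same reason, neither fills the gap.

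Finally, the numbers illustrate a general identity under invented inputs. They do not measure harm to this study. Bland-Altman limits are also not the only paired method. Both points are fair, and the conclusion does not depend on the particular values.

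**Conclusion.** The point holds for the visible agreement subsection. Followed as written, it yields the average bias between devices but not the spread of within-eye differences, so on its own it cannot show agreement, although the paired layout in section 2 can supply what is needed.

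The size cannot be estimated for this trial. Under the assumed values above, one per-device table is compatible with limits about 5.5 units wide (5.8 − 0.2, rounded) or 39.2 units wide (22.6 + 16.6), depending only on the unreported correlation. The conclusion rests on the study eye being measured on both devices, as section 2 describes, and on the visible text. Whether redacted or removed text already holds a paired method is unknown. The change is worth making, with medium confidence because of the redactions.

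**What to change.** In the agreement subsection, state as the agreement analysis, separately by subject population:

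- the within-eye difference, Mirante minus predicate, for each endpoint;
- its mean with a 95% CI;
- Bland-Altman 95% limits of agreement, with CIs for the limits;
- an allowance for repeated pairs when an eye contributes pairs from more than one configuration, for example a random eye effect on the differences.

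Keep the per-device descriptive tables as supportive. If redacted text already specifies this analysis, a cross-reference from the agreement subsection is enough.

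The cost is SAP wording and slight extra programming, with no new data. The downside for the sponsor is that limits of agreement may look less favourable than side-by-side means.

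### Does the SAP have to name what the scan-size and tracing HD measurements from one Mirante are compared with?

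*Combined protocol and SAP*

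**What the plan says.** Section 3, Analysis of Agreement Endpoints, opens with the general rule: "Analysis of the agreement study endpoints will include measurements from Nidek Mirante and the predicate device". The method follows: "Descriptive statistics of each agreement study endpoint will be provided by subject population for each device". A separate paragraph then covers two functions, scan size and tracing HD, whose agreement analysis "will include measurements from one Nidek Mirante and be analyzed in the same fashion as detailed above". This is the only visible mention of scan size or tracing HD.

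The next subsection, on precision, again names both sides: "Analysis of the precision study endpoints will include measurements from the Nidek Mirante and predicate device".

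Section 2 supplies the layout. There are three Mirante units, three Avanti units and one P200DTx. For OCT agreement and precision, "each Nidek Mirante device will be paired with one of the Optovue RTVue XR Avanti devices", and "One device operator will be assigned to each device pair to create three distinct operator/device configurations". The Avanti is listed as the control for OCT and the P200DTx as the control for SLO.

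**The concern.** Agreement is a relation between two sets of measurements, and this sentence supplies one. The sentences on general agreement and precision name both the Mirante and the predicate, and the image-quality sentences each name their pair of devices. Against that pattern, the missing second side could be deliberate or could be shorthand.

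- **Reading A:** settings are compared within the same Mirante, for example two scan sizes, or tracing HD on and off.
- **Reading B:** one Mirante is compared with its paired Avanti.

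The phrase about one Mirante is itself open: one fixed unit for everyone, or one of the three units for each subject.

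The readings use different data and answer different questions. Under B with a fixed unit, any offset belonging to that device pair and its operator stays in the mean difference however many eyes are scanned. Two analysts working from this sentence alone could report different quantities under the same endpoint name.

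**Working it through.** The plan gives no figure to reproduce here. The visible text has no sample size, SD, margin or significance level. The check is therefore mainly one of reading, followed by a look at what the numbers can and cannot show.

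**1. Can the back-reference be carried out?** The only visible method above the sentence is descriptive statistics by population for each device. Applied to one Mirante, it gives one device column; applied to a Mirante and its Avanti, it gives two. Either can be produced from the sentence as written. What is not stated is the agreement contrast. But the visible text states no contrast statistic (paired difference, limits of agreement or otherwise) for the main Mirante and predicate endpoints either. The silence is general to the visible text and not peculiar to these two functions.

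**2. Where would the comparator be defined?** Normally with the endpoints or the scan schedule. The visible text contains neither: no OCT parameter, scan list or objective is given for any endpoint. Section 2 has a redaction and two figures that are not shown, Section 3 has seven redacted blocks, and the part before Section 2 is not available. No redaction falls inside the agreement subsection, but a definition would not be expected there.

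**3. Which reading do the documents favour?** Section 2 sets up Mirante and Avanti pairs for OCT agreement and makes the Avanti the OCT control. The preceding paragraph of Section 3 names the predicate, and the back-reference can carry it forward. That supports B, provided the two functions belong to OCT, which the visible text does not say. A rests on the predicate not being repeated; no visible text describes a comparison of settings within one unit. Neither reading is excluded.

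**4. What would the difference cost?** Let the pair offset have SD *r* in units of the eye-level SD of differences, with *n* eyes and *k* equally weighted pairs. Then Var(mean difference) = *r*²/*k* + 1/*n*.

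- With *k* = 1, the degrees of freedom between pairs are 1 − 1 = 0; with *k* = 3, they are 3 − 1 = 2.
- The offset SD of a single pair is √3 = 1.73 times that of a three-pair mean.
- A 95% interval built from eyes alone would cover the model-level difference with probability 2Φ(1.96/√(1 + *nr*²/*k*)) − 1. With *n* = 40 and *r* = 0.25, one pair gives √(1 + 40 × 0.0625) = √3.5 = 1.871, 1.96/1.871 = 1.048 and coverage 70.5%. Three pairs give 85.2%.
- Over *r* = 0.1 to 0.5 at *n* = 40, coverage runs from 90.2% to 44.5% with one pair and from 93.4% to 65.4% with three.

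Both *r* and *n* are assumptions with no source in the documents, and so is equal weighting of the pairs. The visible SAP plans neither this interval nor a model-level estimand for agreement. Reading A keeps 95% only if the unit offset is purely additive; if the effect of a setting differs between units, one fixed unit has the same limit under A. These figures therefore describe generalising from one device pair. They do not measure the effect of the unclear sentence.

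**The case for a change.** The strongest case for a change is that every comparable sentence in Section 3 names two sides and this one does not. Descriptive statistics on one Mirante would describe that device without assessing agreement, so someone must supply the second set of measurements. Both readings have some support, choosing between them is an assumption, and naming the reference and the unit would take about two sentences.

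Much of this stands. The sentence is thin, and the visible text does not settle which reading is meant. What does not follow is that the plan leads to a wrong result. No stated rule is shown to misfire, and the unclear point is a fact about which scans are taken, which the sponsor and its analysts know from setting up the study.

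Asking in addition for paired differences, confidence intervals and limits of agreement would be a separate preference about method. It presumes paired scans whose existence cannot be confirmed from the available text.

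**Conclusion.** No change to the plan is needed. The sentence leaves out the reference measurement and the identity of the unit, but this is a descriptive detail that the sponsor's analysts can fill from the scan set-up, and the stated method can be run under either reading.

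The effect visible in the documents is small: one device column or two, and, if a fixed unit is set against its Avanti, 1 of 3 configurations. In that last case the result speaks for that device pair and operator, which is a matter of how the result is read.

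This conclusion assumes that the endpoint and scan definitions exist in the full plan or the study set-up, which the redactions and missing parts make plausible but do not prove. If they existed nowhere, the omission would matter more, but the available text cannot show that.
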